7. CONFIRMATION OF RESPONSE AND PROGRESSION

In TRIO026, imaging for confirmation of response (irCR or irPR) is not required.

On the other side, confirmation of progression (irPD) is recommended minimum 4 weeks after the first irPD assessment and is required during the flare time-window of the first 12 weeks of treatment.

8. OTHER CONSIDERATIONS

irPR if no Target Lesions: If new measurable lesions appear in patients with no target lesions at baseline, irPD will be assessed. That irPD timepoint will be considered a new baseline, and all subsequent timepoints will be compared to it for response assessment. irPR is possible if the TMTB of new measurable lesions decreases by $\geq 30\%$ compared to the first irPD documentation.

Symptomatic deterioration: this is not a descriptor of a progressive disease. It may be reason for discontinuation from study treatment but overall response should be based on the objective tumor response according to irRECIST criteria. Subjects with 'symptomatic deterioration' requiring

discontinuation of treatment without objective evidence of disease progression at that time should continue to undergo tumor until objective disease progression is observed.

Doubtful progression: If the Investigator is in doubt as to whether progression has occurred, particularly with regard to non-target lesions or the appearance of a new lesion, it is advisable to continue treatment until the next scheduled assessment or sooner if clinically indicated, and reassess the subject's status. If repeat scans confirm progression, then the date of the initial scan should be declared as the date of progression.

Statistical Analysis Plan

Protocol Title	Phase II randomized study of pembrolizumab with or without epigenetic modulation with CC-486 in patients with platinum-resistant epithelial ovarian, fallopian tube or primary peritoneal cancer
Protocol Number	TRIO026 (Part A) / NCT02900560
	
Revision	01
Product Name	CC-486
Indication	Platinum-resistant epithelial ovarian cancer (EOC), fallopian tube carcinoma (FTC) or primary peritoneal carcinomas (PPC)
Study Phase	II
Sponsor	TRIO
Version Date	10-Apr-2018

Confidentiality Statement

The information contained herein is confidential and proprietary and may not be disclosed, reproduced, or circulated without the prior written consent of TRIO.

Revision History

Not applicable; this is the initial version of the Statistical Analysis Plan.

List of Abbreviations

AE	Adverse Event
CI	Confidence Interval
CM	Concomitant Medications
EOC	Epithelial Ovarian Cancer
FTC	Fallopian Tube Carcinoma
GCIG	Gynecologic Cancer Intergroup
irCR	Immune-related Complete Response
irDCR	Immune-related Disease Control Rate
irNE	Immune-related Unevaluable
irORR	Immune-related Overall Response Rate
irPD	Immune-related Progressive Disease
irPR	Immune-related Partial Response
irRECIST	Immune-related Response Evaluation Criteria in Solid Tumors
irSD	Immune-related Stable Disease
ITT	Intent-to-treat
MedDRA	Medical Dictionary for Regulatory Activities
NCI CTCAE	National Cancer Institute Common Terminology Criteria for Adverse Events
PEM	Pembrolizumab
PPC	Primary Peritoneal Carcinomas
PT	Preferred Term
RDI	Relative Dose Intensity
SAE	Serious Adverse Event
SAP	Statistical Analysis Plan
SOC	System Organ Class
SSC	Study Steering Committee
TRIO	Translational Research in Oncology
WHODD	World Health Organization Drug Dictionary
ULN	Upper Limit of Normal

Title:

TRIO026 (Part A) – Statistical Analysis Plan

1. Introduction

This Statistical Analysis Plan (SAP) describes the detailed statistical methodology for executing the statistical analyses to assess the safety profile of CC-486, fertility evaluation as well as CA-125 response according to TRIO026 protocol version 2.0 for patients enrolled in Part A of the trial. Separate document(s) will be prepared to describe statistical analysis performed on Part B of this trial.

Statistical analysis will be performed by TRIO using SAS® software Version 9.4 or higher.

2. Study Design and Objectives

2.1. Study Design

The protocol synopsis is provided in Appendix 6.1. Refer to protocol for additional details.

2.2. Study Objectives

2.2.1. Primary Objectives

The primary objective for Part A of this study is to establish an optimal schedule of CC-486 combined with pembrolizumab (PEM) in patients with platinum-resistant/refractory EOC. This will be determined based on safety profile, fertility evaluation as well as immune-related Overall Response Rate (irORR)/ immune-related Disease Control Rate (irDCR) per irRECIST criteria.

2.2.2. Secondary Objectives

To assess the CA-125 response based on the Gynecologic Cancer Intergroup (GCI) criteria.

2.2.3. Exploratory Objectives

- Tumor samples will be used to assess potential prognostic or predictive biomarkers, improve understanding of ovarian cancer biology and identify candidate biomarkers that may correlate with treatment benefit and/or safety signals
- Whole blood samples will be used to analyze changes in DNA methylation during treatment with CC-486

Details of methodologies used to assess exploratory objectives will be described in a separate SAP.

2.3. Sample Size

At least 20 patients will be enrolled to TRIO026 Part A. Patients are assigned to one of the following four treatment schedule cohorts in the order they are enrolled in the study (minimum of five patients per cohort):

- Cohort 1: CC-486 100 mg/d, 21 d on, 7 d off + PEM 200 mg iv q3 weeks
- Cohort 2: CC-486 100 mg BID, 21 d on, 7 d off + PEM 200 mg iv q3 weeks

- Cohort 3: CC-486 300 mg/d, 14 d on, 14 d off + PEM 200mg iv q3 weeks
- Cohort 4: CC-486 300 mg/d, 21 d on, 7 d off + PEM 200 mg iv q3 weeks

2.4. Timing of Analyses

The analysis for TRIO026 Part A is conducted when five patients in each cohort are considered evaluable. The criteria for evaluability is described under Section 3.1.3.

3. Statistical Methods

3.1. Analysis Population

3.1.1. Intent-to-Treat Population

The **Intent-to-Treat (ITT) Population** includes all patients who were enrolled in the study, regardless of whether they actually received study medication. All efficacy analyses will be evaluated based on data from this population according to the cohort they were assigned to at enrollment.

3.1.2. Safety Population

The **Safety Population** consists of all patients who receive any study treatment, and will be used for the analysis of safety data of the study. This population will assign patients to the cohort based on the treatment schedule observed in Cycle 1. If this differs from that to which the patient was enrolled, the actual observed treatment schedule will be used for the analysis of safety data.

3.1.3. Evaluable Population

As per protocol version 2.0, the **Evaluable Population** consists of patients in ITT population who also meet the following criteria:

- Completed at least two CC-486 cycles
- Undergone 1st post-baseline tumor burden assessment
- Undergone 2nd tumor biopsy with adequate paired tissue obtained

3.2. Data Handling

3.2.1. Baseline Assessment/Measurement

The last available assessment/measurement of a particular data point on or prior to the latter of the date of enrollment and the date of first dose of study treatment. If patients have no value as defined above, the baseline value will be missing.

3.2.2. Date of First Dose

The date of first dose (of study drug) is derived as the first date when a non-zero and non-missing dose of study drug is administered. This is also referred as the start of the study treatment.

3.2.3. Date of Last Dose

The date of last dose (of study drug) is derived as the last date when a non-zero and non-missing dose of study drug is administered.

3.2.4. Duration

Duration, except for duration of treatment, is calculated as:

- Duration (days): (End Date – Start Date + 1).
- Duration (weeks): (End Date – Start Date + 1) / 7
- Duration (months): (End Date – Start Date + 1) / 30.4375
- Duration (years): (End Date – Start Date + 1) / 365.25

3.2.5. Missing Data

All analyses and descriptive summaries will be based on the observed data. Unless otherwise specified, missing data will not be imputed or “carried forward.”

3.2.6. Partial Dates

Only partial or missing date for Adverse Events (AE) and Concomitant Medications (CM) (including prior and on study systemic anti-cancer therapies) will be imputed according to the following:

3.2.6.1. Imputation Rules for Partial or Missing Stop Dates:

If the month and year are present, impute the last day of that month.

If only the year is present, impute December 31 of that year.

If the stop date is entirely missing, assume the event or medication is ongoing.

If a partial or complete stop date is present and the ‘ongoing’ box is checked, then it will be assumed that the AE or CM stopped and the stop date will be imputed if partial.

3.2.6.2. Imputation Rules for Partial or Missing Start Dates

Start Date		Stop Date						
		Complete: yyyymmdd		Partial: yyyymm		Partial: yyyy		Missing
		< 1 st dose	≥ 1 st dose	< 1 st dose yyyymm	≥ 1 st dose yyyymm	< 1 st dose yyyy	≥ 1 st dose yyyy	
Partial: yyyymm	= 1 st dose yyyymm	2	1	2	1	n/a	1	1
	≠ 1 st dose yyyymm		2		2	2	2	
Partial: yyyy	= 1 st dose yyyy	3	1	3	1	n/a	1	1
	≠ 1 st dose yyyy		3		3	3	3	
Missing		4	1	4	1	4	1	1

- 1 = Impute the date of first dose
- 2 = Impute the first of the month
- 3 = Impute January 1 of the year
- 4 = Impute January 1 of the stop year

3.3. Statistical Analysis

Categorical variables will be summarized in frequency tables, with the counts and percentage of patients in each category. Percentages given in the summary tables will be rounded and thus may not always add up to exactly 100 percent. For continuous variables, summary statistics will include number of patients, mean, standard deviation, first quartile (Q1), median, third quartile (Q3), and minimum and maximum values (range).

3.3.1. Patient Disposition

The patient disposition will be tabulated using the ITT. Frequency count and respective percentages of patients who were in each population (i.e. ITT, Safety, and Evaluable), and discontinued from treatment and/or study will be summarized by cohort. The reason for discontinuation (from treatment and/or from study participation where applicable) will be summarized considering the categories specified in the case report forms. Listings of disposition information and analysis population will be provided as well.

Protocol Deviations including eligibility deviations of the inclusion/exclusion criteria will be summarized and listed for ITT, by cohort.

3.3.2. Demographics and Disease Characteristics

The following patient demographics and disease characteristics will be summarized and listed for the ITT and Safety Population (where applicable) by cohort:

Patient Demographics:

- Age, INT (Date of enrollment – Date of birth) / 365.25
 - INT = integer part
 - Since only the year of birth is collected (YYYY), we assume the full date to be 31-Dec-YYYY
- Race
- Ethnicity
- Weight at Baseline
- ECOG Status at Baseline

Disease Characteristics:

- Time from Initial Diagnosis to Enrollment
- Primary Tumor Location
- Staging at Initial Diagnosis
- Histopathological Type at Initial Diagnosis
- Histopathological Grade at Initial Diagnosis
- Disease Status at Enrollment
- Time from First Progression/Relapse to Enrollment

Prior Surgery for Ovarian Cancer:

Number of patients who underwent prior surgeries will be summarized by type of procedures. A listing will also be done.

Prior Systemic Anti-Cancer Therapy:

Number of regimens of prior systemic anti-cancer therapies will be summarized by type and setting. A listing will be provided to show the specifics of the therapies.

Medical History:

The medical history is coded by the most current version of Medical Dictionary for Regulatory Activities (MedDRA), and will be summarized for ITT by System Organ Class (SOC) and Preferred Term (PT) by cohort.

3.4. Efficacy Analyses

Efficacy data for the primary objective and the secondary objectives will be analyzed for the ITT. Summaries and figures of the efficacy endpoints will be generated by cohort as per enrollment.

3.4.1. Primary Efficacy Objective

Immune-related Overall Response Rate (irORR):

Title: TRIO026 (Part A) – Statistical Analysis Plan

irORR is defined as the proportion of patients achieving a best overall response of immune-related Complete Response (irCR) or immune-related Partial Response (irPR) assessed as per investigator assessment.

$$\text{irORR} = \frac{\text{\# of patients with best overall response as irCR or irPR}}{\text{Total number of patients}}$$

The best overall response outcome (irCR/irPR/irSD/irPD/irNE) will be summarized and tabulated for ITT by cohort.

Immune-related Disease Control Rate (irDCR):

irDCR is estimated based on the proportion of patients in each cohort whose best overall response during the course of study treatment is irCR, irPR or irSD as per investigator assessment.

$$\text{irDCR} = \frac{\text{\# of patients with best confirmed overall response as irCR/irPR/irSD}}{\text{Total number of patients}}$$

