Subjects will be treated in the assigned cohort until progressive disease based on irRECIST, unacceptable toxicity, consent withdrawal or the Investigator concludes that it is in the subject's best interest to discontinue (or any other withdrawal criteria is met according to section 5.5). Subjects who discontinue treatment for reasons different than irPD will enter the follow-up phase and will continue to be followed with tumor assessment every 12 weeks until irPD. After irPD, and provided that subject has undergone the End of Treatment visit, all subjects will be taken off the study unless presence of serious adverse events (SAEs) or study treatment-related adverse events. In such case these events will be monitored as clinically indicated until the events have resolved (or return to baseline) or in the Investigator's opinion, are unlikely to resolve due to the nature of the condition and/or the subject's underlying disease.

Once 5 subjects in each cohort are considered evaluable, enrollment will be stopped and data from each cohort will be analyzed and the optimal schedule to be taken forward into Part B will be selected according to section 3.3.

Part A includes mandatory tumor core biopsies for biomarkers research and mandatory whole blood sampling for DNA methylation analyses (see section 6.4.7).

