5.5 Study Treatment Discontinuation

By default, subjects are treated until progressive disease as per irRECIST (Appendix 2) when study treatment must be discontinued. CA-125 increases should not be used to declare disease progression and/or study treatment discontinuation (refer to section 6.4.6.2).

In Part A and in Arm A of Part B, in case there is a need to permanently discontinue one of the study drugs (whichever the reason), the other one will also be discontinued (i.e. monotherapy with CC-486 or with pembrolizumab is not allowed in Part A and in Arm A of Part B).

The Investigator will also discontinue study treatments if any of the following conditions is met:

- Intercurrent illness or a change in subject's condition or unacceptable toxicity (see section 5.7) that warrants study treatment discontinuation according to Investigator judgment
- Any event, condition, criterion which would warrant discontinuation of pembrolizumab or CC-486 as per section 5.7.
- Any event, condition, reason which would warrant pembrolizumab or CC-486 to be held for more than the maximum acceptable delay as per section 5.7.1.
- Subject completed 24 months of uninterrupted treatment with pembrolizumab or 35 administrations of pembrolizumab, whichever is later (*Note: 24 months is calculated from the date of first pembrolizumab dose*).
- Need for additional local and/or systemic non-protocol anticancer therapy or subject receives non-protocol anticancer therapy at any time during the study treatment
- Subject's decision to withdraw study treatments
- Lost to follow up
- Death
- Pregnancy
- Investigator's decision
- Discontinuation of the study by the sponsor

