12: CT/MRI of chest abdomen and pelvis to be done at each tumor assessment. The schedule of assessments should be fixed according to the calendar, regardless of treatment interruptions. The first post-baseline assessment will be done 6 weeks (\pm 1 week) after first CC-486 intake. Subsequent assessments should be done thereafter every 12 weeks (\pm 1 week) taking as a reference the date of the first post-baseline tumor assessment. Tumor burden assessments will be done according to irRECIST criteria until documentation of irPD regardless of the end of study treatment and start of subsequent anticancer therapy or CA-125 values. Confirmation of progression (irPD) is recommended minimum 4 weeks after the first irPD assessment and is required during the flare time-window of the first 12 weeks of treatment. If there is suspicion of disease progression based on clinical or laboratory findings before the next scheduled assessment, an unscheduled assessment should be performed at the Investigator's discretion. During the follow-up, tumor assessments will only be required in subjects without irPD at time of End of treatment visit.

13: For subjects consenting to this optional tissue acquisition part of the study, a FFPE block/partial block from the EOC debulking surgery will be obtained (or a minimum of 15 unstained slides in case FFPE tissue block cannot be provided).

14: Image-guided core tumor biopsy is mandatory at baseline (within 28 days of study treatment start) and 6 weeks (\pm 1 week) after first CC-486 intake. The second biopsy must be done during the on-treatment period of the 2nd CC-486 cycle. As much as possible and if clinically indicated, the second biopsy should be scheduled to coincide with the 1st post-baseline tumor burden assessment (both 6 weeks \pm 1 week after first CC-486 intake) so the image-guided biopsy is done at the same time the subject undergoes the scans to assess response/progression. If feasible, a fresh-frozen ascites sample will also be collected in subjects with ascites, during the same procedure as the biopsy. Refer to section 6.4.7.1 and the Study Laboratory Manual for additional details.

15: Whole blood for DNA methylation analysis will be obtained via venipuncture. On day 1 of the 1st CC-486 cycle, sample should be obtained prior to the first CC-486 intake.

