6.4.6.1 Schedule/Details of Tumor Burden Assessments

All efficacy endpoints (including the primary and secondary objectives in both Part A and B) are linked to the tumor burden response assessments and therefore the importance of timely and complete disease assessments in this study cannot be understated. Failure to perform any of the required disease assessments will result in the inability to determine disease status for that time point. Frequent off schedule or incomplete disease assessments have the potential to weaken the conclusion of this clinical trial.

The schedule of tumor burden assessments should be fixed according to the calendar, regardless of treatment interruptions. Tumor burden assessments will be performed until progressive disease as per irRECIST regardless of the discontinuation of study treatment, the start of a subsequent anticancer therapy or CA-125 values.

The same method of assessment and the same technique used at baseline (CT scan or MRI) to characterize each lesion must be used at each subsequent post-baseline assessment. Review of post-baseline scans and assessment of overall response (according to irRECIST) should be done at the next visit after the scans are performed and prior to indicating subsequent study therapy, to rule out progressive disease that would warrant study treatment discontinuation.

The irRECIST guidelines for measurable, non-measurable, target and non-target and the tumor response criteria are presented in Appendix 2.

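### Part A irORR has no assessment window, so a response on later anticancer therapy can be credited to the assigned CC-486 schedule

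*SAP*

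**What the plan says.** - **irORR.** SAP 3.4.1: "irORR is defined as the proportion of patients achieving a best overall response of immune-related Complete Response (irCR", with irPR also counting. It is tabulated for ITT by assigned cohort (SAP 3.1.1, 3.4). No first or last eligible scan is given, and nothing is excluded after new therapy. The definition in the protocol synopsis has no cut-off either.
- **irDCR.** The same SAP section counts patients "whose best overall response during the course of study treatment is irCR, irPR or irSD". The synopsis definition of irDCR has no such limit, so the SAP added one for irDCR only.
- **Scanning.** Protocol 6.4.6.1 continues tumor assessments to irPD "regardless of the discontinuation of study treatment, the start of a subsequent anticancer therapy or CA-125 values". Footnote 12 to Table 6 (Protocol 6.2.1) repeats this for Part A.
- **Who is affected.** Protocol 3.1: "Subjects who discontinue treatment for reasons different than irPD will enter the follow-up phase and will continue to be followed with tumor assessment". These scans come at 12-week intervals and end at irPD.
- **How a subject stops before irPD.** Protocol 5.5: "in case there is a need to permanently discontinue one of the study drugs (whichever the reason), the other one will also be discontinued". The same section lists need for, or receipt of, non-protocol anticancer therapy as a reason to stop.
- **Confirmation.** Appendix 2, section 7: "imaging for confirmation of response (irCR or irPR) is not required".
- **Use.** Step 2 of Protocol 3.3 bases the choice on toxicity and irORR, with irDCR and correlative data as possible additions.
- **Available data.** SAP 5.2 lists on-study systemic anticancer therapies with start dates. SAP 3.4.1 does not use those dates.

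**The concern.** Best overall response is meant to describe what the assigned schedule did. With no end to the window, a tumor reduction produced by a different treatment can enter the numerator for that schedule. Part A picks the regimen for the experimental arm of Part B from four cohorts with a minimum of five subjects each, so a single response carries weight. The two paired endpoints also use different windows, so the set of responders need not be contained in the set with disease control, as it should be.

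**Working it through.** Part A states no power, alpha or calculated sample size (Protocol 8.7), so there is no figure of the plan to reproduce. The check is a reading of the text, followed by an illustration of size.

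**1. Trace one subject through the text.** She stops without irPD, for example for toxicity, and stays in tumor follow-up (Protocol 3.1). Other anticancer agents are barred only until the End of Treatment visit (Protocol 5.6.2), so she may then start one. A later scheduled scan shows TMTB at least 30% below study baseline, which is irPR under Appendix 2, section 6. No confirmation is needed, so her best overall response is irPR and she is an irORR success for her assigned cohort. She counts in irDCR only if irSD or better was recorded during study treatment. If she stopped before the week-6 scan, she is in irORR and not in irDCR.

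**2. Shift from one such response,** 1/n with n the cohort's ITT size:
- n = 5: 1/5 = 20 points
- n = 6: 1/6 = 16.7 points
- n = 8: 1/8 = 12.5 points

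Five is the minimum. Non-evaluable subjects are replaced (Protocol 3.1) but remain in ITT.

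**3. Chance of at least one such response in a cohort,** 1 − (1 − r)^k. Here k is the number starting new therapy before irPD and r is its response rate. The documents do not give k, so 1 to 3 is assumed. The synopsis puts current options below 15-20%, so r = 10-20% is taken.

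| r | k = 1 | k = 2 | k = 3 |
|---|---|---|---|
| 10% | 10.0% | 19.0% | 27.1% |
| 15% | 15.0% | 27.8% | 38.6% |
| 20% | 20.0% | 36.0% | 48.8% |

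**4. Effect on the ranking, given one extra response.** Assume independent cohorts of five with the same true irORR p. Take p = 10-20%, around the 11.5% cited for pembrolizumab in Protocol 1.4.1. Add one response to one given cohort and sum the exact binomial probabilities.

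| Cohorts compared | p | Becomes sole leader | Moves from behind into a tie for first |
|---|---|---|---|
| 4 | 10% | 32.3% | 40.3% |
| 4 | 11.5% | 30.7% | 39.2% |
| 4 | 20% | 25.8% | 32.9% |
| 2 | 10% | 46.2% | 21.8% |
| 2 | 11.5% | 42.8% | 22.5% |
| 2 | 20% | 32.0% | 22.9% |

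**5. Rough combined size.** Multiply the chance in step 3 by the chance of a new sole leader in step 4:
- Four cohorts: 0.10 × 0.258 = 2.6% to 0.488 × 0.323 = 15.8%
- Two cohorts: 0.10 × 0.320 = 3.2% to 0.488 × 0.462 = 22.5%

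This takes the extra response as exactly one, in a subject not already a responder, and follows one given cohort only.

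**The case against.** **Intent.** SAP 5.1 plans one table giving best overall response, irORR and irDCR, and SAP 5.2 lists one best overall response per patient. A single shared window may well have been intended. But the SAP does not state it, and a programmer following 3.4.1 literally would apply the limit to irDCR alone.

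**Exposure is narrow.** This stands. Only subjects who stop before irPD are affected, because tumor follow-up ends at irPD. New therapy is barred until about 30 days after the last dose, scheduled scans after week 6 are 12 weeks apart, and irPR needs a 30% fall from study baseline. All of this must happen before the analysis. Against that, accrual is planned over about 24 months, so early enrollees may have several scans after stopping.

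**The committee would notice.** Part A is exploratory, the Steering Committee also weighs toxicity, and its Charter is not among the documents. Dated scans and therapy dates are listed, so such a response could be found among some 20 subjects. That limits the harm but does not correct the tabulated irORR.

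**Stronger readings.** A reader might infer that the gap favours the more toxic schedule. The documents do not support this. Step 1 removes cohorts on toxicity before irORR is compared. In the Step 2 example the higher irORR wins only when toxicity is similar, and ties go primarily to the more favorable profile. Schedule 1, the lowest dose, allows no dose reduction (Table 3), so several toxicities that lead to a reduction elsewhere lead to discontinuation there.

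A reader might also infer that one misattributed response would often decide the choice, since at 11.5% a cohort of five has 0.885^5 = 54% chance of no response. One cohort's chance of zero is not a ranking result. Over the quoted confidence interval of 2.4-30.2% it also runs from 0.976^5 = 89% down to 0.698^5 = 17%.

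**Conclusion.** The concern holds. As written, SAP 3.4.1 lets a single unconfirmed irPR on later therapy count for the assigned schedule, and nothing elsewhere in the protocol or SAP closes the gap. Such a response moves irORR by 12.5 to 20 points for ITT sizes of eight down to five. It can change the ranking but need not. The tendency is toward schedules with more stops before irPD, which are not necessarily the more toxic ones.

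The 10-49% chance of at least one such response per cohort rests on the assumed one to three subjects and the assumed 10-20% response rate. The ranking figures further assume equal true rates and five subjects per cohort. The flaw in the definition depends on none of these assumptions. It should be corrected before the Part A analysis.

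**What to change.** In SAP 3.4.1, define best overall response once, for irORR, irDCR and the Step 1 futility count. It is the best irRECIST response from first dose to the earliest of (a) irPD, (b) start of subsequent anticancer therapy, and (c) data cut-off. Specify that irPD in (a) means confirmed irPD wherever the protocol requires confirmation, that is, in the first 12 weeks of treatment. The week-6 scan falls in that period, and Appendix 2 notes that response may follow an initial increase in tumor burden. Ending the window at an unconfirmed early irPD would discard such responses. List responses after the window separately.

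The cost is one SAP sentence and possibly a slightly lower irORR. Therapy start dates are already listed, so no new data are needed. Part B should set its window in its own SAP: it admits subjects without target lesions, for whom Appendix 2, section 8 allows irPR after irPD, so this wording cannot simply be carried over.
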